6.4 SUBJECT SETS ANALYSED

The following analysis sets are defined for this trial:

- Screened Set (SS): consists of all subjects who signed informed consent.
- Treated Set (TS): consists of all subjects that have been randomized and that received at least one administration of study drug. The TS will be the main analysis set for the evaluation of safety. Subjects are analysed according to the actual received treatment.
- Full analysis set (FAS): consists of all subjects in TS that have a baseline and at least one evaluable post-baseline measurement for the primary endpoint. This is the main analysis set for the evaluation of efficacy data.
- Per protocol set (PPS): This is a subset of FAS, for subjects with adequate protocol compliance. It consists of all subjects in FAS without any important protocol deviations that impact efficacy assessments.

- Adherent set (AS): consists of all subjects in FAS that are at least 60% overall adherent to study medication. See Section 7.3.2 for further information.

c42059532-01

[figure not shown]
Proprietary confidential information © 2023 Boehringer Ingelheim International GmbH or one or more of its affiliated companies.

Table 6.4: 1 Subject sets analyzed

	Subject set					
Class of analyses	TS	SS	FAS	PPS	PKS	AS
Primary and secondary endpoints, compliance			Х	X*		
Further endpoints (Х			
Disposition		Х				
					Х	
Safety variables and iPDs	Х					
Demographics, baseline characteristics, exposure	Х			(X)		
Primary endpoint adjusted for overall study						Х

* If the percentage of subjects in FAS with iPD that lead to the exclusion from the PPS is > 10%, then sensitivity analysis of the primary and secondary efficacy endpoints using PPS may be conducted.

(X) An additional PPS presentation of the demographic/baseline endpoints may be provided in the End of Text (EoT) section, if there are a non-negligible number of treated subjects with no post randomization data for the primary endpoint.

Proprietary confidential information © 2023 Boehringer Ingelheim International GmbH or one or more of its affiliated companies.

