7.2 PLANNED ANALYSES

7.2.1 General considerations

The following patient analysis sets are defined for this trial:

- Full Analysis Set (FAS): includes all randomized patients who received at least one
 dose of trial medication during the trial and had a baseline and at least one postbaseline observation for the primary or secondary endpoints. The FAS is used for
 efficacy analyses and patients in FAS are analysed under the randomized trial
 medication.
- Treated Set (TS): includes all patients who signed informed consent and were treated with at least one dose of the trial medication. Patients in TS are analyzed under the actual trial medication received at randomization. The TS is used for safety analyses as well as demographics and baseline characteristics.

Data from patients who were screened but not randomized will be listed but not included in any summary or inferential statistics.

In general, baseline values are the last measurements taken prior to the first administration of trial medication at randomization (Visit 2), (see Flow Chart 1). Further details (e.g., the handling of randomized patients that receive the wrong treatment) will be provided in the TSAP.

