5. ENDPOINTS(S)

5.1 **PRIMARY ENDPOINT(S)**

Change from baseline in Clinician-Administered PTSD Scale for DSM-5 (CAPS-5) total severity score at Week 8

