5.2.2 Secondary endpoint(s)

CAPS-5

- Response defined as ≥30% CAPS-5 reduction from baseline at Week 8

[figure not shown]
- Response defined as ≥50% CAPS-5 reduction from baseline at Week 8

PCL-5

- Change from baseline on the PTSD Checklist for DSM-5 total score at Week 8

c42059532-01

Proprietary confidential information © 2023 Boehringer Ingelheim International GmbH or one or more of its affiliated companies.

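### The SAP defines the full analysis set more narrowly than the protocol, so patients with post-baseline PCL-5 but no usable CAPS-5 drop out of the PCL-5 analysis

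*SAP*

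**What the plan says.** Protocol 7.2.1 builds the FAS from randomised patients who took at least one dose and have a baseline and "at least one postbaseline observation for the primary or secondary endpoints". It uses this set for efficacy and analyses patients under their randomised medication.

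SAP 6.4 starts from the treated set (TS: randomised, at least one dose). It then says that the FAS "consists of all subjects in TS that have a baseline and at least one evaluable post-baseline measurement for the primary endpoint", and adds: "This is the main analysis set for the evaluation of efficacy data". The SAP's primary endpoint is "Change from baseline in Clinician-Administered PTSD Scale for DSM-5 (CAPS-5) total severity score at Week 8". Two of the three secondary endpoints are CAPS-5 responses; the third is "Change from baseline on the PTSD Checklist for DSM-5 total score at Week 8".

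In SAP Table 6.4:1 the row "Primary and secondary endpoints, compliance" is marked for the FAS, with the per-protocol set (PPS) as a conditional sensitivity set. The partly redacted row for further endpoints is also marked for the FAS. SAP 7.5.2 models PCL-5 in the same way as the primary endpoint and names no other analysis set.

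Footnote (X) to the table offers an extra baseline table on the PPS "if there are a non-negligible number of treated subjects with no post randomization data for the primary endpoint".

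**The concern.** SAP Section 3 states that the SAP rests on Section 7 of the protocol, yet the two current texts give different membership rules for the main efficacy set. Two programmers, each following one document, could report different FAS counts.

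The patients in the gap have observed data. PCL-5 is the only secondary endpoint not derived from CAPS-5, and protocol 7.2.8 counts secondary results among the evidence for the sponsor's decision at the interim analysis. Under the SAP, a valid PCL-5 value is discarded because a different instrument is missing. The PPS and the adherent set are subsets of the FAS and inherit the exclusion.

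Two details add ambiguity. *Evaluable* is not defined for the FAS. The SAP also does not repeat the protocol's rule that FAS patients are analysed as randomised, while the treated set from which it builds the FAS is analysed by treatment received.

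**Working it through.** **Baseline check of the plan's own figures.** Protocol 7.5 assumes 30% drop-out. 200 / (1 − 0.30) = 285.7, rounded up to 286; 120 / (1 − 0.30) = 171.4, rounded up to 172. Both match the protocol, and neither changes if the FAS definitions are aligned.

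**The definitions side by side.**

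| Element | Protocol 7.2.1 | SAP 6.4 |
|---|---|---|
| Randomised, at least one dose | yes | yes (through the TS) |
| Baseline | yes | yes |
| Post-baseline data | primary or secondary endpoint | primary endpoint only, and *evaluable* |
| Treatment assignment for the FAS | as randomised | not stated |

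**Who falls between them.** Two of the secondary endpoints are computed from CAPS-5. The only way to have secondary data without primary data is therefore a post-baseline PCL-5 with no usable post-baseline CAPS-5.

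**Can that happen?** Flow Chart 2 schedules both instruments post-baseline at Visits 6 and 10 and at the early end-of-treatment visit. Protocol 6.2.2 puts PCL-5 first. It takes 5 to 10 minutes, whereas the CAPS-5 interview takes 45 to 60 minutes and needs a qualified clinician rater (protocol 5.2 and 5.3). PCL-5 without CAPS-5 at a visit is possible. To fall outside the SAP's FAS, a patient must lack a usable CAPS-5 at every post-baseline visit attended, so the group is probably small.

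**Which analyses change.**
- Primary CAPS-5 model: a patient with no post-baseline CAPS-5 has no change score to contribute. No effect from the missing reference to secondary endpoints.
- CAPS-5 response at 30% and 50%: SAP 6.6 does not impute missing response. No effect.
- PCL-5 model: the patient is included under the protocol and excluded under the SAP.
- Further endpoints: the same exclusion applies to any that are not CAPS-5 measures; the row is partly redacted.

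**Size.** The documents give no count, so the affected share p is an assumption, with k = p × 286. If each excluded patient would have supplied a full Week 8 PCL-5 value on top of 200 others, leaving them out multiplies the standard error by √((200 + k) / 200).

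| Assumed p | k | Standard error ratio |
|---|---|---|
| 0% | 0 | 1.000 |
| 1% | 2.9, about 3 | 1.007 |
| 2% | 5.7, about 6 | 1.015 |
| 5% | 14.3, about 14 | 1.034 |

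**The case against.** The strongest reply is that little depends on this. The primary result is untouched, two of three secondary endpoints are untouched, both instruments share all their visits, and protocol 7.1 plans no formal hypothesis test. All of that stands, and it limits the point to a definition that should be aligned.

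A reader might infer more than the documents support:

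- **That *evaluable* means CAPS-5 within 7 days of the last dose, so that off-treatment CAPS-5 is lost to the supplementary estimand.** SAP 6.3 censors measurements from the primary analysis; it does not remove patients from the FAS. SAP 6.7 maps efficacy data collected after early discontinuation to later visits. The SAP's only definition of the term, for the interim analysis in 7.9.3, asks for a patient still in the study with at least one CAPS-5 change score and sets no on-drug condition. The supplementary-estimand analysis is not visible in the public SAP. What stands is that the term is undefined for the FAS and open to misreading.
- **That an early leaver has only one chance to enter the FAS.** Protocol 3.3.4.1 asks patients who stop drug to attend all remaining visits, or at least the early end-of-treatment visit and Visit 10. The inference fits only someone who leaves the study altogether.
- **That exclusion depends on tolerating a long interview.** The interview length makes the gap possible. Neither document shows why CAPS-5 would be missing.
- **That the change from the protocol is unacknowledged.** The public SAP shows no Section 4, and a recorded change could sit in text that is not available.
- **That baseline balance goes unreported.** Baseline is tabulated on the treated set, as protocol 7.2.1 specifies, and the footnote (X) table is optional. The footnote is only a small mismatch: its trigger describes patients in the TS but not the FAS, while the PPS is defined by important protocol deviations.

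**Conclusion.** The mismatch is real and lies in current text. SAP 6.4 requires a post-baseline CAPS-5 where protocol 7.2.1 accepts data for the primary or a secondary endpoint. Following the SAP therefore drops observed PCL-5 data that the protocol would analyse. The consequence is confined to the PCL-5 model and to any further endpoints not based on CAPS-5.

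The size is probably small: 0 to 14 patients and at most about 3% in the PCL-5 standard error. This rests on the assumed 0 to 5% share, on 200 patients otherwise contributing at Week 8, and on every excluded patient supplying a Week 8 value. The last assumption makes the precision loss an upper figure within that range. Confidence is high for the difference in wording and low for the count. It is worth correcting because the correction is nearly free, not because the trial's main conclusion is at risk.

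**What to change.** In SAP 6.4, restore the protocol's FAS: at least one dose, a baseline and at least one post-baseline observation for the primary or a secondary endpoint, analysed as randomised. Delete *evaluable* from the definition, so that membership cannot be read as requiring on-treatment CAPS-5 and the censoring in SAP 6.3 acts only on measurements. Optionally, move the footnote (X) baseline table from the PPS to the FAS, which is the set its trigger concerns.

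The cost is SAP wording, one change to the set derivation and, if the option is taken, one baseline table. No sample-size figure changes. The change is best made before treatment codes are released.

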6.6 HANDLING OF MISSING DATA AND OUTLIERS

Missing data are not explicitly imputed and remain missing for all main analyses. For efficacy endpoints which are continuous in nature, the use of a restricted maximum likelihood (REML)-based mixed model repeated measures (MMRM) approach will ensure that missing data are handled implicitly via a missing at random assumption (MAR) by the statistical model. For the binary efficacy endpoint of CAPS-5 response, missing data will not be imputed.

Missing or incomplete AE dates are imputed according to BI standards (see "Handling of missing and incomplete AE dates") (5). Missing data and outliers of data are handled according to (6).

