6. GENERAL ANALYSIS DEFINITIONS

6.1 **TREATMENT(S)**

For details on the treatment regimen, assignment of treatment groups, and the selection of doses, refer to Section 4 of the CTP. Below in Table 6.1:1 are the descriptions of the short and long names of the treatments. Next, are the definitions of the study phases for the analysis periods (Table 6.1:2).

Table 6.1: 1 Treatment descriptions

Long Name	Short Name	
Placebo	Placebo	
BI 1358894 125 mg qd	BI 125 mg	

Table 6.1: 2 Study analysis phases*

Study analysis phase	Description	Start Date (included)	End Date (included)
Screening phase	Screening (prior to treatment)	Date of informed consent	Date of first treatment administration minus 1 day
Treatment phase and residual effects period	On-treatment period	Date of first treatment administration	Date of last treatment administration + REP
Follow-up phase	Off-treatment period	Date of last treatment administration + REP +1 day	Date of last CTP visit

* The defined treatment periods are the same for all treatment groups.

REP is the residual effect period which is defined as 28 days after the last dose of trial treatment for safety, and 7 days after last dose for efficacy

Dates are defined individually per patient. If more than one date is associated with a specific visit, measurements associated with a specific date are assigned to a study analysis phase according to the rules specified in the table. An analysis phase will not extend beyond the start date of the following phase.

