However, ICEs 6-9 are handled using the hypothetical approach, where measurements after their occurrences are therefore censored in the primary analysis. Therefore, this analysis (ICEs 6-9) will include all data collected while on treatment which is defined as the time from the date of the first dose of trial medication until the date of the last dose of trial medication plus 7 days. Any data collected after a patient discontinues trial drug, regardless of reason, will be censored and will not be included in the primary analysis.

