6.7 BASELINE, TIME WINDOWS AND CALCULATED VISITS

Baseline is defined as the last observation at, or prior to Visit 2. Hence, if a subject is randomized at Visit 2, but does not start trial medication until a future visit (e.g., Visit 4), then his/her baseline is the latest assessment performed at Visit 2. However, for laboratory safety measurements, the last value prior to the first drug administration will be considered as the baseline value.

Planned and actual test days are included in the analysis data sets and are calculated relative to the beginning of treatment as indicated in Table 6.7: 1 below.

For efficacy measurements, only one observation per time window will be selected for statistical analysis –the first one in the corresponding time window. If there are two observations which have the same difference in days to the planned day, or if there are two observations on the same day, the first value will be selected. If an observation is available on the last day of treatment, this observation will be preferably selected over any later observation that is still within the time window. Assignment of efficacy observations to visits based on time windows will be based on the non-imputed (observed) data. Repeated and unscheduled efficacy measurements will be assigned to the nominal visits according to the time windows described in Table 6.7: 1.

For safety measurements, data collected at all visits will be used. For repeated and unscheduled safety measurements for the same visit on treatment, the worst of these will be selected for analysis. In the case for which there is no standard reference direction for the safety parameter, the average of all values for the same visit will be used for analysis.

Visit	Relative to treatment start	
	Planned test day	Actual test day
2	1	Day 1 – Day 2

Table 6.7: 1Planned and actual study days

c42059532-01

Proprietary confidential information © 2023 Boehringer Ingelheim International GmbH or one or more of its affiliated companies.

3	8	Day 3 – Day 12
4	15	Day 13 – Day 19
5	22	Day 20 – Day 26
6	29	Day 27 – Day 33
7	36	Day 34 – Day 40
8	43	Day 41 – Day 47
9	50	Day 48 – Day 52
10/EOT	57 for completed subjects	Day 53 – treatment stop date (stopdt) + 7 days
eEOT	N/A (for early discontinued subjects)	Date of the last administration of trial medication + 7 days (for early discontinued subjects).

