7.4 PRIMARY OBJECTIVE ANALYSIS

7.4.1 Main analysis

The primary endpoint is the change from baseline to Week 8 in CAPS-5 total score. Baseline refers to the measurement recorded at randomization (Visit 2), if data at Visit 2 is missing, then data from Visit 1 will be considered baseline. The primary analysis of the primary endpoint will use a hybrid estimand that combines the treatment policy and hypothetical estimands as detailed in Section 6.3.

MMRM analysis

The change from baseline in CAPS-5 total score at Week 8 for each dose group as well as the corresponding variance-covariance matrix are estimated by a mixed effects model repeated measure (MMRM) including the fixed categorical covariates of treatment, and the stratification indicator of presence of significant childhood trauma (yes vs. no), the continuous fixed covariates of baseline CAPS-5 total severity score and time since index event (in years) and the treatment-by-visit interaction. Patient is considered as a random effect. Visit will be treated as a repeated measure with an unstructured covariance matrix used to model the within subject variability. The Kenward-Roger approximation will be used to estimate the denominator degrees of freedom. Analyses will be implemented using SAS 9.4 PROC MIXED. FAS is used for the primary analysis of the primary efficacy endpoint.

More specifically, the change in CAPS-5 total score from baseline (Visit 2), at Visits 2, 6, and 10 (Weeks 0, 4, and 8) will be evaluated using an MMRM accounting for the following sources of variation: 'treatment', 'visit', 'presence of significant childhood trauma (yes vs.no), time since index event (in years) and 'baseline CAPS-5 total score' as continuous covariates, and treatment-by-visit interaction, as well as the random 'subject' effect. The methods described in Section 10.1 will be utilized to resolve model non-convergence.

SAS code for MMRM:

The following SAS code will be used to calculate the MMRM.

PROC MIXED DATA=indata cl method=reml;

CLASS visit trt stratum subject;' MODEL ept = stratum visit*trt time_since_index base / ddfm=kr s CL; REPEATED visit / subject= subject type=un r rcorr; LSMEANS visit*trt / pdiff=all om cl alpha=**0.05** slice=visit;

RUN;

Results of the MMRM (N, mean, SE and 95% CI per dose group and timepoint) will be presented in tables and displayed graphically.

c42059532-01

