7.5.2 Secondary objective analysis

Logistic regression analysis

[figure not shown]
The binary secondary endpoints of CAPS-5 response (defined as \geq 30% CAPS-5 reduction from baseline at Week 8 and defined as \geq 50% CAPS-5 reduction from baseline at Week 8) will each be analyzed through a logistic regression model to obtain an estimate of the population odds ratio (OR) and associated confidence intervals between active arms and placebo. This logistic regression will be adjusted for fixed factors of treatment and presence of significant childhood trauma (yes vs. no). The analysis will be performed on the FAS. Adjusted odds ratios together with 95% confidence intervals will be used to quantify the effect of treatment, comparing treatment to placebo.

The SAS code for the logistic regression model is as follows:

```
proc logistic data=indata;
class trt stratum/ param=GLM; /* include (ref="placebo") for trt*/
model resp = trt base stratum / link=LOGIT covb;
lsmeans trt / cl;
run;
```

Adjusted odds ratio together with 95% confidence intervals, comparing all treatments to placebo, will be presented.

The secondary endpoint of change from baseline in PTSD Checklist for DSM-5 (PCL-5) total severity score at Week 8 will be analyzed using an MMRM model like that described for the primary analysis of the primary endpoint to obtain the adjusted change from baseline at Week 8 for BI active arm versus placebo.

Proprietary confidential information © 2023 Boehringer Ingelheim International GmbH or one or more of its affiliated companies.

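### CAPS-5 response is analysed on observed Week 8 cases only, so its odds ratio is biased if the rate of drop-out, or its relation to Week 4, differs by arm

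*SAP*

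**What the plan says.** SAP 6.6 treats one instrument in two ways. Continuous efficacy endpoints go through an MMRM that handles missing values under MAR. For response the rule is: "For the binary efficacy endpoint of CAPS-5 response, missing data will not be imputed".

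- **Who is in the analysis set.** Under SAP 6.4 the FAS "consists of all subjects in TS that have a baseline and at least one evaluable post-baseline measurement for the primary endpoint". A Visit 6 score alone is enough.
- **Primary model.** SAP 7.4.1: the change in CAPS-5 "at Visits 2, 6, and 10 (Weeks 0, 4, and 8) will be evaluated using an MMRM". The Week 4 score contributes.
- **Response model.** SAP 7.5.2 fits a logistic regression on the FAS for each response definition at Week 8. The text adjusts for treatment and the childhood-trauma stratum. The code reads "model resp = trt base stratum / link=LOGIT covb", which adds baseline. Neither contains Week 4.
- **Intercurrent events.** Protocol 7.2.2 sets the strategy for the primary endpoint and Protocol 7.2.4 extends it to PCL-5. No strategy is stated for response. The efficacy residual period ("and 7 days after last dose for efficacy", footnote to SAP Table 6.1:2), the on-treatment definition for the primary analysis ("until the date of the last dose of trial medication plus 7 days", SAP 6.3) and the end of the Visit 10 window ("treatment stop date (stopdt) + 7 days", SAP Table 6.7:1) suggest that later off-drug scores are not Week 8 data. The early-EOT row of the same table, however, maps scores collected after discontinuation to later visits.

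**The concern.** Response is the CAPS-5 change cut at a threshold, yet patients whose Week 4 result informs the primary estimate drop out of the response comparison. If those who leave differ from those who stay, the observed response rate in that arm shifts. If the shift differs between arms, so does the odds ratio.

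Symmetry cannot be taken for granted. SAP 6.3 lists withdrawal for lack of efficacy and withdrawal for drug-related adverse events among the events of interest, and Protocol 1.2 reports more headache on BI 1358894 than on placebo. Neither document predicts drop-out by arm. At stake are two of the three secondary endpoints. Both are also in the interim package (SAP Table 7.9.3:1), where Protocol 7.2.8 lets secondary results support the decision to stop or continue.

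**Working it through.** **1. The plan's own figure.** Protocol 7.5 plans 200 evaluable patients with 30% drop-out: 200/0.7 = 285.7, rounded up to 286. This reproduces, and leaves 86 patients without evaluable data.

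**2. Which patients are treated differently.**

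| Usable scores after baseline | MMRM | Response odds ratio |
|---|---|---|
| Week 8, with or without Visit 6 | in | in |
| Visit 6 (Day 27–33), no Week 8 | in | out |
| Only scores mapped to Visits 3–5 or 7–9 | out | out |

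Only the middle row is at issue.

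**3. How many.** The share of the 86 with a Visit 6 score is not given.
- All: 86/286 = 30% of MMRM patients (upper bound)
- Half: 43/243 = 18%
- A quarter: 22/222 = 10%
- None: 0%

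**4. Full-data odds ratio, ≥30% response.** From Protocol 7.5: standardized effect 0.35. Assumed, not in the documents: SD of change 12 (effect 0.35 × 12 = 4.2), baseline mean 42 (SD 7) independent of change, placebo improvement 8 at Week 4 and 12 at Week 8, two-thirds of the effect at Week 4.
- A patient responds if improvement − 0.3 × baseline ≥ 0. The SD of that margin is √(12² + 0.3² × 7²) = √148.41 = 12.18.
- Placebo: mean margin 12 − 12.6 = −0.6, so Φ(−0.6/12.18) = 0.480.
- Active: mean margin 16.2 − 12.6 = 3.6, so Φ(3.6/12.18) = 0.616.
- Odds ratio (0.616/0.384)/(0.480/0.520) = 1.604/0.923 = 1.74.

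**5. Observed-case odds ratio.** Let drop-out after Week 4 have log-odds a + s × (Week 4 score in SD units, higher is worse), with a set in each arm to give the stated rate. Slope s is 1.0 unless noted; Week 4–Week 8 correlation is 0.5–0.7. Unadjusted odds ratios by simulation, at the 30% upper bound:

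| Drop-out pattern | Observed-case odds ratio |
|---|---|
| Same slope, same rate | 1.76–1.78 |
| Active slope half of placebo, same rate | 1.55–1.61 |
| Same slope, 20% active / 40% placebo | 1.46–1.54 |
| Same slope, 40% active / 20% placebo | 2.01–2.16 |
| Placebo only related to Week 4 | 1.32–1.43 |
| Active only related to Week 4 | 2.16–2.37 |

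The third and fourth rows show that an equal relation is not enough. The arm that loses more patients is more strongly selected for those doing well, so its observed response rises further.

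A separate calculation with a weaker slope (0.7), correlation 0.5–0.8 and placebo response of 30% or 50% gives the same pattern. The observed-case to full-data ratio is 1.00–1.03 (same slope and rate), 0.86–0.91 (same slope, 20%/40%), 0.78–0.86 (placebo only) and 1.16–1.32 (active only).

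**6. Fewer missing.** In trial-sized simulations (2000 per scenario, equal rates, full-data odds ratio 1.75–1.79), the half-slope pattern gives 1.58–1.65 at 30% missing, 1.66–1.69 at 18% and 1.69–1.73 at 10%. At correlation 0.6 the bias is about 0.3, 0.2 and 0.1 standard errors. For one-arm dependence it reaches about 0.9, 0.6 and 0.4.

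**7. Imputing Week 8 from Week 4.** In those simulations multiple imputation gives 1.74–1.80 throughout. In the two unequal-rate cases of step 5 it gives 1.72–1.74. If drop-out instead follows status at Week 6 (correlation 0.6, 30% missing), correction is partial: 1.62 (placebo only) and 1.99 (active only), against full-data 1.77–1.78.

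**The case against.** The rule is prespecified and contradicts nothing in the protocol, which sets no missing-data rule for binary endpoints. Observed-case analysis of secondary, descriptive endpoints in a proof-of-concept trial without formal testing is a defensible choice. The interim decision rests mainly on the CAPS-5 standardized effect, which the MMRM already covers. The larger figures need strongly asymmetric drop-out that no passage predicts, and the Phase I adverse events were mild or moderate. All of this stands and limits the weight of the point.

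Three further objections stand in part. If off-drug Visit 10 scores count for response, fewer patients are missing; the documents do not settle this. The all-patients denominator in SAP 7 is a default with exceptions allowed, so tabulated percentages may, not must, differ from the model's denominator. Imputation from Week 4 does well in step 7 partly because drop-out there was driven by Week 4.

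A reader might also infer more than the documents support:
- **That the response result will favour the drug.** The direction depends on which arm loses which patients.
- **That 30% of patients are lost to the odds ratio.** That is the upper bound.
- **That precision suffers badly.** With random drop-out at correlation 0.6, imputation lowers the mean reported standard error by only 5%, 2% and 1% at 30%, 18% and 10% missing.
- **That no sensitivity analysis is planned.** SAP 6.6 speaks of the main analyses, and parts of the SAP are not visible.

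**Conclusion.** The point holds as a conditional one. The two response odds ratios discard Week 4 information that the primary analysis of the same score uses. They are nearly unbiased only if both the drop-out rate and its relation to Week 4 match across arms. If either differs, the bias at the upper bound runs from modest (about 1.74 to 1.55–1.61) to material (1.46–1.54 or 2.01–2.16), with one-arm dependence as extremes. These sizes rest on the assumed SD, means, correlation and drop-out slopes; only the effect size and overall drop-out come from the protocol.

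It does not follow that the primary result or the proof-of-concept decision is compromised: the MMRM is untouched and response is only supporting evidence. This is a worthwhile, inexpensive improvement rather than a critical error.

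**What to change.** Replace the response sentence in SAP 6.6 and amend 7.5.2:

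1. State that response follows the primary estimand's intercurrent-event handling, with on-treatment data running to last dose plus 7 days. This settles the status of off-drug Visit 10 scores.
2. Multiply impute Week 8 CAPS-5 under MAR from treatment, stratum, baseline, time since index event and Week 4. Patients with neither a Visit 6 nor a Week 8 score can be left out, as in the MMRM; using their last on-treatment early-EOT score is optional.
3. Derive ≥30% and ≥50% response in each imputed data set, fit the logistic model with treatment, stratum and baseline, and combine by Rubin's rules.
4. Report response percentages from the same imputed data, so that table and model share a denominator.
5. Keep observed-case analysis and non-responder imputation as sensitivity analyses, if not already planned in a part of the SAP that is not visible. Non-responder imputation is not a neutral main analysis: with the same relation and rate in both arms and 30% missing it gives 1.48–1.49.
6. Align the 7.5.2 text with its code on baseline.

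The cost is SAP wording and a short PROC MI / MIANALYZE step, with no new data. The downsides are some programming, dependence on a seed, and only partial correction if drop-out follows worsening after the last observed score.
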